After an overnight fast (> 10 hours), study subjects will report to LSU Exercise Physiology Laboratory to complete V4. V4 will be scheduled 48 hours after the subject's last training session. During this visit, we will measure height, weight and vital signs. During this visit, we will ask subjects to complete the International Physical Activity Questionnaire-Elderly,¹⁹ Sedentary Behavior Questionnaire,²⁰ and PROMIS Physical Function Questionnaire^{21, 22}, and the Pittsburgh Fatigability Questionnaire. We will also measure the body composition by DXA and BIA. We will also perform the MMTT as described for V1. We will also draw fasting and MMTT associated bloods as described for V2 (total blood volume of about 150 ml or 10-12 tablespoons total). The analyses performed on these blood samples collected in V4 will be as described for V2.

Posttraining V5 (About 3.5-4 hours)

After an overnight fast (> 10 hours), study subjects will report to PBRC to complete V5. V5 will be scheduled about 72 hours after the subject's last training session. During this visit, we will measure height, weight and vital signs. We will measure body composition using standard circumferences, optical imaging, and BIA, which will be conducted in [name] Laboratory. During this visit, we will collect a fasting blood sample (~ 10 ml). We will also perform the MRI for leg muscle mass, Phosphorous Magnetic Resonance Spectroscopy – ³¹P-MRS, and Muscle Biopsy as described for V3. During V5, subjects who agree to the optional Carbon-13 magnetic resonance spectroscopy procedure will do that procedure.

STUDY ENDPOINTS

Primary Endpoints

1. Comparison of within and between group changes in muscle strength, mass, and quality (strength/mass) using isokinetic dynamometry and DXA (primary outcomes Aim 1) between treatment groups.
2. Comparison of within and between group changes in body composition by DXA, fasting blood glucose and lipids by a clinical chemistry panel and glucose tolerance by a mixed meal tolerance test (primary outcomes Aim 2)

Safety Endpoints

1. Safety will be monitored by adverse event reporting (See Data Safety Monitoring Plan).

DETAILED METHODS AND ANALYSIS

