
PBRC Fasted Blood Draw. During the Screening Visit, Part I, and post-training V5, blood will be drawn to measure complete blood counts (CBC), clinical chemistry (Chem 15) and blood lipids. These measurements will be conducted in the PBRC Clinical Chemistry Core.

LSU Mixed Meal Tolerance Test (MMTT), LSU Blood Draws, and Storage (about 4 hours). After an overnight fast (≥ 10 h), an intra-venous (IV) line will be placed in the arm vein for blood drawing purposes by trained and medically certified personnel (e.g., a certified phlebotomist, licensed medical personnel, [name], PhD, or [name]). The IV will remain there throughout the testing. A fasting blood sample (~50 ml or 10 teaspoons) will be drawn and then the subject will drink about 2 cups of Boost (82 g of carbohydrates, 8 g of fat, and 20 g protein).³⁴ Blood samples will be drawn at 0, 10, 20, 30, 60, 90, 120, 150, and 180 min post-ingestion to measure plasma glucose, insulin, and c-peptide. We will draw about 150 ml or 10-12 tablespoons of blood for this test in total, including the fasting blood draw. During the IV procedure, a small amount of the subjects own blood (less than 1 teaspoon) may be immediately returned into his/her vein through the IV after each specimen is collected. During the MMTT the subjects will be in a semi-recumbent position on an examination table. In the event of a vasovagal response, we will place the subject in a supine position with their legs elevated. The subjects will be provided water to increase fluid intake. We will also monitor his/her blood pressure closely. The PI and medical investigator will be notified. We will also assess their standing pulse rate and blood pressure and ensure they feel okay again before releasing them. After initial processing, fasting and post-ingestion plasma glucose will be measured immediately using the glucose oxidase method (Anolox GL5) and a portion of the fasting and post-ingestion plasma samples will be stored at -80°C for batch measurements of hormones (e.g., insulin and c-peptide). We will use the trapezoidal rule to determine the glucose and insulin AUCs, and the Oral Minimal Model to calculate the SI and Φ .^{26, 35} A portion of the fasting whole blood sample will be used to isolated PBMCs and T-Cells. Moreover, after initial processing, fasting serum samples will be stored at -80°C for batch measurements of pro-inflammatory cytokines. Left over samples will be stored at -80°C for future research purposes. We may also assess heart rates using heart rate monitors (e.g., Polar or Zephyr Bioharness) during the MMTT.

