molecule called ¹³C-acetate. An IV line will be placed in a vein in of the subject's arm. A port will be placed in a vein of the subject's other arm so that a 2 mL (0.4 teaspoons) sample of blood may be drawn before and every 10 minutes during the procedure for a total of 18-20 mL (3.5-4 teaspoons) of blood. The IV line will be used to infuse the solution at a predetermined rate (e.g. 15 mg/kg/min as bolus followed by 6 mg/kg/min for the remainder of the scan). The solution will begin to enter the vein and may continue to flow until the scan is over. We will then use Carbon-13 Magnetic Resonance Spectroscopy (¹³C-MRS), to measure *in vivo* skeletal muscle biochemical dynamics. These measurements will be performed in the PBRC Imaging Core. This test involves measurement of ¹³C-labeled TCA cycle metabolites and acetylcarnitine-acetyl CoA shuttling in the muscle. The aim of this test is to calculate the rates of TCA cycle metabolic flux and levels of acetylcarnitine and acetyl. Prior to testing, study subjects must have fasted for at least 10 hours. This scan will take approximately 95 minutes in total to complete. Subjects will be positioned supine on the 3.0 T magnet with only the lower extremity inside the bore. The ¹³C RF coil will be positioned over the right *vastus lateralis* (or left if the person has a medical reason not to use the right leg). The ankles and femur will be secured to each other with Velcro or nylon sports straps to create some resistance for the dynamic kicking exercise required for the test. A scout scan is performed first in order to visually locate the *vastus lateralis* muscle. Next, ¹³C spectra are acquired for 20 minutes while the subject rests in the scanner. The subject will then be infused with the ¹³C-acetate followed by ¹³C spectra acquisition for 75 minutes. After 60 minutes of infusion, the participant will be instructed to kick against the strap or a force sensor for 12 second periods followed by 12 second rest periods in repetition for the remainder of the scan (about 15 minutes). It is possible that the participant may experience muscle fatigue earlier than the 15 minutes. This scan is for research purposes only and not for diagnostic treatment.

STUDY TIMELINES

The anticipated duration that each subject will actively participate in this study is about 5-6 months, which includes initial screening, baseline assessments (V1, V2), 16 week intervention period, and post testing assessments (V3, V4, V5).

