11. **Muscle Biopsies.** A *vastus lateralis* muscle biopsy will be performed using the technique of Bergstrom as described in SOP 906 from the PBRC Inpatient Unit by a trained Nurse Practitioner or physician. For *vastus lateralis* muscle biopsies, the risks are mild to severe pain, soreness, bruising and a small scar are common risks. There is a small risk of a hematoma (collection of blood in the tissue) or infection at the biopsy site. There is also a slight risk that a superficial nerve may be cut; the nerve may heal, or it may result in a permanent loss of sensation in the skin at the biopsy site. Sterile technique will be used to minimize infection risks and the biopsy site will be monitored closely. To reduce the risk of hematomas and bleeding, we ask that subjects stop taking anticoagulants, non-steroidal anti-inflammatory (NSAIDs), and aspirin for a week before and after the biopsy procedure. We will exclude individuals who cannot stop their anticoagulants. Previous data suggest that the rates of adverse events following a percutaneous muscle biopsy in older adults (60-76 years) are similar to those of younger adults.⁴¹ Moreover, [name] previously conducted a study at PBRC that included biopsies in elderly adults (70-84 years) with no serious adverse events.⁴² The PI has led and been involved in multiple studies that included muscle biopsies in both young (18-30) and older adults (65-85 years).^{15, 43-45}
12. **Archive of Biological Sample (blood and muscle biopsy tissue).** The primary risk to subjects who donate bio-samples to be banked for future research (molecular in this case) is the risk of loss of confidentiality and/or privacy. Most banks need to maintain a link between the identities of donors and coded specimens to be able to collect valuable clinical follow-up information about the donor. We will, however, create and maintain a firewall between the source and the researcher so that the protected health identifiers are never given to the researcher(s). Storage and disposal of tissue will be conducted in a manner conforming to the appropriate care and handling of biological specimens as outlined through the Institutional Biohazard Committee Guidelines.

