collected at LSU, and we will enter the data into a RedCap database under the direction of the study team's biostatistical consultant. We will routinely transfer the original data collection forms (e.g., questionnaires) from LSU to PBRC to ensure that each subject's records are up to date. The PI, Co-I's, medical consultant, and biostatistical consultant will review all data. The privacy of the study subjects is very important to PBRC, LSU, our study team, and we will protect the privacy of the study subjects as much as possible. In compliance with HIPAA requirements, we will not send out the names, addresses, phone numbers, social security numbers, or any other identifying information on our study subjects. If study data and / or study samples are sent outside of the LSU for further analysis, these data and / or samples will be de-identified. Similarly, any publications generated from the data collected from the proposed studies will exclude identifiers.

3. Data Safety Monitoring Plan (DSMP)

Overview of DSMP. Efforts to minimize the potential risks of the assessment methods and outcome variables include frequent monitoring by the investigators to assure that no volunteer suffers any adverse effects from participating in the research. The study team has extensive experience in all procedures and aspects of the study. The study team will review any subject safety issues as they occur and monthly research meetings. We will use an investigators committee to review the safety data in aggregate once a month. Our investigators committee will include the PI, Co-I's, and medical director ([name]). The PBRC's Institutional Review Board will also continuously monitor the proposed study for subject safety throughout the study period.

Safety Monitoring. In this study, an **adverse event or experience** is defined as any health-related unfavorable or unintended medical occurrence that happens throughout study participation. Examples of adverse events include but are not limited to the following:

- A clinically significant laboratory or clinical test result.
- An event that results in missing a study visit.
- An event that requires a visit to a physician.
- An event that occurs as a result of a study procedure.
- Unanticipated or untoward medical events that are not plausibly pregnancy related and may be study related.

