LSU and PBRC is committed to ensuring and maintaining the safety of its subjects. We will use the AAHRPP provided definitions of Adverse Events and Serious Adverse Events. We will report adverse events according to the institutional reporting policy provided by AAHRPP.

A **serious adverse event** (SAE) is defined as an unanticipated medical occurrence that is deemed associated with study participation by the study Medical Investigator that results in one of the following:

- Death
- Life-threatening event
 - Life threatening events in the mother or fetus are defined as those that in the view of the research staff and PI put the individual patient at imminent substantial risk of dying, or if continued participation in the study might have resulted in death.
- Hospitalization
- Disability or permanent damage
- Medical Intervention to prevent permanent impairment or damage

All AEs from date of consent will be reported. Adverse events will be documented during the scheduled visits. For each sign, symptom or adverse event, the following information will be recorded:

- A brief descriptor of the adverse event
- Start and stop dates
- Intensity (mild / moderate / severe)
- Whether the AE was "serious" or not (as defined below)

- Causal association with the intervention assigned (none / doubtful / possibly / probably / very likely)
- Outcome (resolved / resolved with sequelae / improving / still present and unchanged / death)
- Action taken with respect to the intervention (none / intervention temporarily discontinued / medical therapy required / intervention permanently discontinued / other).

Adverse event data will be collected from the date of consent until the final visit. Adverse event data will be analyzed quarterly, but serious or life-threatening adverse events may require immediate reporting and follow-up. We anticipate most adverse events will be mild and the subject will be able to resume activities within a day or two of reporting the event. Adverse Event reporting will follow the requirements of the IRB. Only adverse events that qualify as unanticipated problems will be reported to the IRB. Unanticipated problems involving risks to subjects or others include incidents only if the incident is unexpected, related or possibly related to participation in the research, and indicated that subjects or others are at a greater risk of harm than was previously known or recognized.

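### Adverse event collection closes at V5, the visit of the second muscle biopsy and last blood draw, with no later contact scheduled to pick up delayed harms

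*Combined protocol and SAP*

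**What the plan says.** The Safety Monitoring text of the Data Safety Monitoring Plan (DSMP) sets the window, "Adverse event data will be collected from the date of consent until the final visit", and the means, "Adverse events will be documented during the scheduled visits". Study Timelines ends with "and post testing assessments (V3, V4, V5", and Table 1 has no column after V5.

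The description of V5 includes the MRI, the spectroscopy "and Muscle Biopsy as described for V3". (The biopsy procedure is actually described under V2; the cross-reference to V3 does not affect this point.) Under PBRC Fasted Blood Draw, a panel is taken at screening "and post-training V5, blood will be drawn to measure complete blood counts (CBC", along with clinical chemistry and lipids.

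Item 11 of Potential Risks lists haematoma, infection and a cut superficial nerve with possibly permanent loss of sensation. It then says: "Sterile technique will be used to minimize infection risks and the biopsy site will be monitored closely". It also asks subjects to stop anticoagulants, NSAIDs "and aspirin for a week before and after the biopsy procedure".

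The DSMP counts events caused by a study procedure as adverse events, and also "A clinically significant laboratory or clinical test result". Study Endpoints gives one safety endpoint, which rests on adverse event reporting.

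**The concern.** The biopsy is the most invasive procedure in the study, and the harms the protocol names for it mostly declare themselves after the subject has gone home. For the second biopsy, the collection window closes at the visit where the procedure is done. A site infection some days later, or sensory loss that proves lasting, would be recorded only if the subject chose to report it and the team chose to record it outside the stated window.

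At stake are the completeness of the only stated safety endpoint and the promise to monitor the biopsy site. The subjects are aged 65 to 80, and a lasting deficit could meet the DSMP's own seriousness criterion for disability or permanent damage. The DSMP also requires a stop date and an outcome for every event. For an event still open at V5, nothing is scheduled that would supply them.

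**Working it through.** There is no stated figure for this point to reproduce, so the check sets the schedule against the collection window and then sizes the gap.

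**Schedule against window**

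- End of collection: the final visit (DSMP). Final visit: V5 (Table 1, Study Timelines).
- Second biopsy and last blood draw: V5 (Posttraining V5; PBRC Fasted Blood Draw).
- Scheduled collection time after the V5 visit: 0 days.
- The protocol's own post-biopsy periods: a precaution of one week after the procedure (Potential Risks, item 11), and at least 5 days of recovery between the V2 biopsy and the start of training (Exercise Interventions).

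The protocol thus treats a biopsy as having consequences for days afterwards, but schedules no observation over those days for the second one. The first biopsy differs. Training starts between 5 days and 6 weeks after V2, and supervised sessions then run twice weekly for 16 weeks, with clinical symptoms assessed before each (Exercise Interventions in the human-subjects section; Potential Risks, item 18). V2 harms therefore fall inside the window and have repeated contacts at which they can surface.

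**Number of biopsies affected**

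Inputs, from Study Population and the sample size section: 12 completers in each of 3 groups, 20% attrition, up to 45 enrolled.

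- Enrolment: 12 / (1 − 0.20) = 15 per group, and 3 × 15 = 45, which agrees with the plan.
- Completers: 3 × 12 = 36.

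Randomization follows V2, so I assume that all 45 have the first biopsy and that the 36 completers have the second.

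- Total biopsies: 45 + 36 = 81.
- Share with no scheduled ascertainment after the procedure visit: 36 / 81 = 44%.

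| First biopsies | Second biopsies | Share |
|---|---|---|
| 45 | 36 | 36/81 = 44% |
| 45 | 30 | 30/75 = 40% |
| 36 | 36 | 36/72 = 50% |
| 45 | 45 | 45/90 = 50% |

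The range is about 40% to 50%, so the result depends little on retention.

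**Laboratory results**

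The V5 sample is drawn inside the window, and a clinically significant result is an adverse event under the DSMP. No turnaround time is given. A result available on the day can be recorded at V5. For one that comes back later, no step is described that brings it into the adverse event record.

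**The case against.** The strongest reply is that the protocol does not leave subjects unobserved. Pain, bleeding or a vasovagal reaction at V5 occurs within a scheduled visit. At screening, subjects receive office and mobile numbers for study staff. The DSMP has safety issues reviewed as they arise and monthly, and says serious events may need immediate reporting and follow-up. MRI abnormalities have their own route through a radiologist to the Medical Investigator. The biopsy follows SOP 906, which is not reproduced in the protocol and may contain aftercare, as may the consent form. The one-week period is a medication precaution, not a defined risk window for adverse events.

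Much of this stands, and it limits the point. A reader might infer that harms of the second biopsy are never collected, or that its recorded complication rate would be near zero. The documents do not support that, because events during V5 and spontaneous reports can be recorded. For the same reason, one cannot say that only 45/81 of complications would be captured; that would need zero capture of every V5 event, immediate ones included. Nor does the text show that every V5 panel reports after the window closes. The panel is not labelled a safety panel either, and clinical chemistry also serves primary outcomes. Nothing says that biopsy safety data will go forward to the R01; the pilot is to supply effect sizes for outcomes. The V2 biopsy needs no extra call on this evidence.

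What does not stand is the suggestion that these routes close the gap. None schedules a contact after V5 or moves the stated end of collection. Telephone numbers and review of issues as they arise depend on the subject volunteering a problem after leaving the study. An aftercare procedure in an SOP would still need a protocol window in which to record what it finds.

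**Conclusion.** The point holds as one about planned ascertainment. Followed as written, the protocol has no scheduled means of learning about delayed harms of the second biopsy, the outcome of events open at V5, or V5 laboratory abnormalities that result after the visit. This does not fit its undertaking to monitor the biopsy site closely.

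The gap covers about 36 of 81 biopsies (44%, range about 40% to 50%), on the assumption that all 45 enrolled are biopsied at V2 and 36 reach V5. How many events would be missed cannot be estimated, because the documents give no complication rate and no rate of spontaneous reporting. The conclusion also assumes that neither SOP 906 nor the consent form schedules a later contact that feeds the adverse event record; the sponsor can check this quickly. It is a modest flaw in a stated rule, cheap to correct, and it should be corrected.

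**What to change.** Reconcile the V5 description, item 11 of Potential Risks and the Safety Monitoring text of the DSMP. End adverse event collection at a scheduled telephone contact after V5 instead of at V5. The sponsor should set the timing so that it is consistent with the post-biopsy period already in item 11; no duration is proposed here. At that contact, record:

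- any delayed event related to the biopsy;
- the status of events still open at V5;
- any clinically significant V5 laboratory result.

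Add the contact to Table 1 and to Study Timelines.

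The cost is about 36 short calls by existing staff, one per completer, and a wording change in the protocol and consent form. It needs no new procedure or clinic visit.
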